### **Statistical analysis**

Balance of randomized HES and albumin groups on potentially confounding baseline and procedural characteristics will be assessed using absolute standardized difference (ASD), defined as the absolute difference in means, mean ranks, or proportions divided by the pooled standard deviation. We define any variable with  $ASD > 0.25$  as imbalanced and will adjust for such variables in the following analyses. This substudy will be modified intent-to-treat, including all patients who enrolled in SHARP.

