### **Experimental Protocol**

Cardiac surgical patients enrolled in the SHARP study will be randomized to either 5% human albumin or 6% HES on entrance to the operating room. Anesthetic and Surgical management will follow protocol established by SHARP study including administration of a blinded study solution which contains 5% human albumin or 6% HES following separation from cardiopulmonary bypass. Blood will be collected for measurement of baseline syndecan 1 and endocan following arterial line and urinary catheter placement. At 1 and 24 hours following surgery completion, blood will be collected for measurement of syndecan 1 and endocan. Within two hours of ICU arrival, PAT will be performed in ICU. In a subset of patients, PAT will be performed preoperatively and at 24 hours after surgery.

Because vasoactive substances may influence EndoPAT measurement, we will collect data on use of all preoperative antihypertensive medications that have direct or indirect effect on smooth muscle relaxation. Cardiac surgery patients often need intraoperative and postoperative inotropic support. Data on use of perioperative vasoactive medications that may influence EndoPAT results including epinephrine, norepinephrine, vasopressin, milrinone, nitroglycerine, nitroprusside, and sedatives such as propofol, dexmedetomidine and others will be recorded and subsequently adjusted for in the analysis. Data on transfusion of packed red blood cells and blood components will be collected from Anesthesia Record Keeping System. Minimum hematocrit (HCT) will be approximately 23% following cardiopulmonary bypass and 21% on cardiopulmonary bypass. Packed blood cell, platelets, fresh frozen plasma and/or cryoprecipitate transfusions may be administered as determined necessary by attending anesthesiologist or surgeon. Any imbalance in blood product transfusion between the two study groups will be adjusted for in analysis.

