### ***Primary analysis***

We will estimate the albumin effect on RHI using multivariable linear regression adjusting for imbalanced patient and procedure characteristics. Though we expect RHI to be normally distributed, appropriate transformations will be made if this is not the case (e.g., log transformation). If transformations are not successful, we will use nonparametric methods (i.e., Wilcoxon rank-sum test).

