### **Secondary analyses**

The albumin effect on each biomarker (i.e., syndecan 1 and endocan) at 1 hour and 24 hours after surgery will be assessed using separate repeated measures linear regression models adjusting for within-subject correlation, baseline biomarkers and imbalanced baseline variables. We will assess the heterogeneity of the treatment effect over time by testing the group-by-time interaction for each model using a criterion of  $P < 0.15$ . If heterogeneity is detected, we will analyze outcomes separately at each time, using additional Bonferroni correction as necessary. We expect that biomarkers will be lognormally distributed, so we will perform a log transformation and compare groups on ratio of geometric means. An alpha of 0.05 will be used for each set of the primary and sub/secondary analyses, with a significance criterion of 0.05 for the primary analysis and 0.0125 for each sub or secondary analysis (i.e., 0.05/4, Bonferroni). We will complete analyses using SAS version 9.4 or newer (SAS Institute, Cary, NC, USA) and R version 3.2.3 or newer (R Project for Statistical Computing, Vienna, Austria).

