### **Sample size analysis**

This will be limited to the 85 patients expected to enroll in the SHARP study. Moerland et al found the a mean  $\pm$  SD of  $1.8 \pm 0.5$  in a healthy study population and  $2.9 \pm 1.4$  in a population with renal injury [M. Moerland, A. J. Kales, L. Schrier, M. G. J. van Dongen, D. Bradnock, and J. Burggraaf, "Evaluation of the EndoPAT as a Tool to Assess Endothelial Function," International Journal of Vascular Medicine, vol. 2012, Article ID 904141, 8 pages, 2012. doi:10.1155/2012/904141]. We expect similar variability in our cardiac surgery population. Assuming a conservative standard deviation of 1.4, we will have 90% power at the 0.05 significance level to detect an difference of 1.0 or greater in our study population. We will have 65% power to detect a clinically important difference of 0.73 (i.e., 25% of 2.9).

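### Baseline covariates for the primary RHI model are picked by observed imbalance (ASD > 0.25), which chance alone exceeds for about one variable in four at n = 85; the model can fall short of the stated power, and fixed covariates do as well or better

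*Combined protocol and SAP*

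**What the plan says.** - **Screening rule (Statistical analysis).** Baseline and procedural characteristics are compared between arms by ASD. A variable above 0.25 is classed "as imbalanced and will adjust for such variables in the following analyses". No list of candidate variables is given.
- **Primary model (Primary analysis).** RHI is analysed by "multivariable linear regression adjusting for imbalanced patient and procedure characteristics". This section names no baseline covariate that is always included.
- **Biomarker models (Secondary analyses).** These are fitted "adjusting for within-subject correlation, baseline biomarkers and imbalanced baseline variables", so the baseline biomarker is always in the model.
- **Drugs (Experimental Protocol).** Because vasoactive substances may affect the EndoPAT reading, "we will collect data on use of all preoperative antihypertensive medications that have direct or indirect effect on smooth muscle relaxation". The same paragraph commits to adjusting for perioperative vasoactive drugs and sedatives, with no imbalance condition. The Primary analysis section does not mention this.
- **Power (Sample size analysis).** "This will be limited to the 85 patients expected to enroll in the SHARP study". "Assuming a conservative standard deviation of 1.4", "we will have 90% power at the 0.05 significance level to detect an difference of 1.0 or greater". "We will have 65% power to detect a clinically important difference of 0.73". These figures concern RHI only and make no allowance for covariates.

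**The concern.** In a randomised trial, baseline differences between arms arise by chance. Adjustment gains precision when a covariate predicts the outcome, whether or not it is imbalanced. Selecting on observed imbalance reverses this. A variable that does not predict RHI but differs between arms enters the model and, being correlated with treatment in that sample, widens the standard error. A variable that does predict RHI but happens to be balanced stays out, and its precision gain is lost.

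Two things are at stake. The first is power, which the plan already puts at only 65% for the difference it calls clinically important. The second is pre-specification: which covariates enter cannot be known until the arms have been compared, and it depends on how many variables are screened.

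**Working it through.** **Inputs.** From Sample size analysis: N = 85, SD = 1.4, alpha = 0.05, differences 1.0 and 0.73. From Statistical analysis: cut-off 0.25. Assumed because not stated: 1:1 allocation (42/43), a two-sided test, all 85 analysed, the number of candidates screened, and the share of RHI variance they explain (R²).

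**1. The plan's own power.** The standard error of the unadjusted difference is 1.4 × √(1/42 + 1/43) = 1.4 × 0.217 = 0.304. A two-sample t-test on 83 degrees of freedom has power 90.2% for 1.0 and 66.1% for 0.73 (65.5% for 0.725, which is exactly 25% of 2.9). The stated 90% and 65% are reproduced by the unadjusted test. A one-sided test would give 95.0% and 77.6%, which does not fit.

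**2. How often chance crosses 0.25.** The SD of a standardised difference under randomisation is 0.217, and 0.25/0.217 = 1.15. The chance of exceeding the cut-off is 2 × (1 − Φ(1.15)) ≈ 24.9% (25.2% by t; 26–28% for binary variables; about 30% if only 70 patients are analysed). A cut-off crossed 5% of the time would be 1.96 × 0.217 = 0.425. On average 10 × 0.25 = 2.5 of 10 candidates are flagged, or 5.0 of 20. A given prognostic variable is left out 1 − 0.249 ≈ 75% of the time.

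**3. Power of the planned model against fixed adjustment.** The ASD columns come from simulation (85 patients, independent normal candidates, thousands of runs per setting, R² carried by three or four candidates). The last column can be approximated by hand for four fixed covariates: SE = 0.304 × √(1 − R²) × √(1 + 4/78), and power = Φ(difference/SE − 1.99). For R² = 0 and 0.73: SE = 0.304 × 1.025 = 0.311; 0.73/0.311 = 2.35; Φ(0.36) = 64%. For R² = 0.3: SE = 0.304 × 0.837 × 1.025 = 0.261; 0.73/0.261 = 2.80; Φ(0.81) = 79%. Simulation agrees.

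Power (%) for 0.73 / 1.0:

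| R² (assumed) | ASD rule, 5 candidates | ASD rule, 10 | ASD rule, 20 | Four fixed covariates |
|---|---|---|---|---|
| 0 | 64 / 89 | 62 / 87–88 | 58–59 / 84 | 64 / 89 |
| 0.1 | 65 / 90 | 64 / 89 | 60 / 86 | 68 / 92 |
| 0.2 | 67 / 91 | 65 / 90 | 61 / 87 | 73–74 / 94 |
| 0.3 | 69–70 / 93 | 67–68 / 91–92 | 62–63 / 89 | 79–80 / 97 |

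For 0.73, the gap in favour of fixed adjustment is nil with 5 noise candidates and about 2–5 points with 10–20. It is about 3–9 points at R² 0.1 (5 to 20 candidates) and about 8–17 points at R² 0.2–0.3 (10 to 20 candidates).

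**4. Type I error.** Under the ASD rule it is about 5% with noise candidates and about 3–4% at R² 0.3. It stays near 5% with fixed covariates.

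**The case against.** A fair defence makes five points.

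- **The shortfall is not certain.** A reader might infer that the model must miss 65%/90%. The documents do not support that: they give neither the number of candidates nor their R². Ten candidates at R² 0.3 meet the stated figures, and five noise candidates cost only 1–2 points. This objection stands.
- **R² may be low.** Sub-aim 1 reports that preoperative endothelial function correlates poorly with postoperative function. If so, the 8–17 point gain may not materialise. This stands too, although a low R² leaves the loss from noise covariates at 10–20 candidates intact.
- **Selection is not wholly by ASD.** The Experimental Protocol adjusts for perioperative vasoactive drugs and sedatives unconditionally. The present point therefore covers pre-treatment variables only. Whether preoperative antihypertensives fall under that commitment is unclear, and the Primary analysis section does not resolve it.
- **The biomarker models differ.** A reader might carry the power argument over to them. They always contain the baseline biomarker, and the 65%/90% figures are not about them.
- **Validity is intact.** The threshold is stated in advance and uses no outcome data. A reader might infer bias or false positives. Over repeated randomisations chance imbalance averages to zero, and the type I error is at or below 5%.

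The plan also screens variables it regards as potential confounders, so an entirely non-prognostic pool is the unfavourable end of the range. None of these points gives a reason to prefer the ASD trigger: in the settings examined, fixed covariates matched or beat it.

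**Conclusion.** The concern holds as a matter of efficiency and pre-specification, not of validity. The 25% chance rate and the match of the stated power to an unadjusted t-test are firm, given 1:1 allocation and 85 analysed patients. That the planned RHI model can fall short of 65%/90% is also established. That it will do so is not, because this turns on an unstated candidate list and an unknown R². The better-supported loss is relative to fixed adjustment, and its size depends on the assumed R² and number of candidates. The change is worth making before unblinding.

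**What to change.** 1. **Statistical analysis and Primary analysis.** Replace the ASD trigger with a short list of pre-treatment covariates, fixed before unblinding and always in the RHI model. Candidates already available: age, planned concomitant CABG, preoperative antihypertensives acting on smooth muscle, and baseline log syndecan 1 (drawn before the study solution is given).
2. **Secondary analyses.** Keep the baseline biomarker and use the same fixed list in place of the imbalance-selected variables.
3. **ASD table.** Report it as a description of balance. An ASD-selected model may be kept as a labelled sensitivity analysis.
4. **Experimental Protocol against Primary analysis.** Reconcile the commitment to adjust for vasoactive drugs and sedatives with a primary model that does not mention them, and say which analysis it belongs to.
5. **Sample size analysis.** State that 65% and 90% are for the unadjusted comparison.

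This is a wording change and needs no new data. The cost is about 2 points of power if the four covariates prove non-prognostic (about 64%/89% against 66%/90% unadjusted). That is no worse than the ASD rule with five noise candidates, and better than the rule with ten or more.

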## EXPERIMENTAL METHODS AND DATA ANALYSIS

### Research Design and Methods

This investigation will represent a substudy of a current ongoing clinical trial (SHARP: Voluven vs. Albumin comparing effect of 5% human albumin vs. 6% HES (130/0.4) on postoperative kidney function and coagulation. Patients who consent for SHARP study will be invited for participation in this substudy of endothelial/glycocalyceal function.

**Inclusion criteria:** Patients aged 40 – 85 years old who signed a written, informed consent for participation in this investigation, scheduled for elective aortic valve replacement with or without coronary artery bypass grafting involving nonpulsatile cardiopulmonary bypass, with or without additional minor surgical procedure.

**Exclusion criteria:** Patients with Raynaud's disease or other disease associated with upper extremity vascular insufficiency, and inability to perform EndoPAT exam (inability to lie still for 15 min, or significant finger deformity), patients meeting SHARP exclusion criteria (renal failure with oliguria or anuria not related to hypovolemia, dialysis, preoperative creatinine > 1.6 mg/dL, anticipated deep hypothermic circulatory arrest, known hypersensitivity or allergy to HES, clinical conditions with volume overload e.g., patients in pulmonary edema or congestive heart failure, severe hypernatremia or severe hyperchloremia, intracranial bleeding, pregnant or breast feeding women, critically ill adult patients e.g. patients who are hospitalized in the intensive care unit prior to surgery, severe liver disease, pre-existing coagulopathy).

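### Does describing the analysis set as all SHARP enrollees, when the substudy has its own consent and EndoPAT criteria, alter the primary analysis or its power?

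*Combined protocol and SAP*

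**What the plan says.** The Statistical analysis section defines the population in one sentence: "This substudy will be modified intent-to-treat, including all patients who enrolled in SHARP". It does not say what the modification is.

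Research Design and Methods sets the entry conditions. Recruitment is by a further invitation: "Patients who consent for SHARP study will be invited for participation in this substudy of endothelial/glycocalyceal function". Inclusion requires that the patient has "signed a written, informed consent for participation in this investigation". Upper-limb vascular disease and "inability to perform EndoPAT exam (inability to lie still for 15 min, or significant finger deformity") are exclusions listed apart from those inherited from SHARP.

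On timing, Experimental Protocol says that patients "will be randomized to either 5% human albumin or 6% HES on entrance to the operating room", and that the primary measurement comes later: "Within two hours of ICU arrival, PAT will be performed in ICU".

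On the model, Primary analysis says: "We will estimate the albumin effect on RHI using multivariable linear regression adjusting for imbalanced patient and procedure characteristics". Covariates are chosen by a balance check: "Balance of randomized HES and albumin groups on potentially confounding baseline and procedural characteristics will be assessed using absolute standardized difference (ASD"), with a threshold of 0.25. No section gives a rule for a patient without an RHI.

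The Sample size analysis takes the 85 patients expected in SHARP and an SD of 1.4, which it calls conservative. It states 90% power for a difference of 1.0 and 65% for 0.73, the latter being 25% of 2.9.

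**The concern.** Read literally, the population sentence admits patients whom the eligibility criteria keep out: those who decline the substudy and those who cannot have the EndoPAT examination. An undefined modified intention-to-treat set could leave the denominator to be chosen after the data are seen.

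Two consequences would matter if they were real.

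- **Bias.** Randomization precedes the ICU measurement, so an RHI can go missing after treatment. If that happened more often, or in sicker patients, in one arm, the comparison of patients with a measurement could be distorted. Refusals and exclusions settled before randomization do not carry this risk; they cost only precision and generalisability.
- **Power.** The calculation uses every expected SHARP enrollee. Any refusal, exclusion or failed reading reduces the number analysed, so at an SD of 1.4 the stated power is a best case.

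**Working it through.** **1. The two readings side by side.** The literal reading is all SHARP enrollees. The narrow reading is SHARP patients who joined the substudy. The question is who can contribute to a regression with RHI as the outcome.

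| SHARP patient | Has an RHI? | In regression, literal reading | In regression, narrow reading |
|---|---|---|---|
| Declined the substudy or excluded for EndoPAT reasons | No | No | No |
| In the substudy, RHI obtained | Yes | Yes | Yes |
| In the substudy, RHI missing | No | Not unless imputed | Not unless imputed |

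The plan mentions no imputation, so the rows that enter the model are the same on both readings. The set could change which patients enter the balance check, and so which covariates are selected. Checking balance in all randomized substudy patients and checking it in those with an RHI are both defensible.

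**2. Reproducing the stated power.** Inputs from the Sample size analysis: N = 85, SD 1.4, alpha 0.05, differences 1.0 and 0.73 (unrounded: 0.25 × 2.9 = 0.725). Assumed because not stated: a two-sided test and near-equal arms (42 and 43).

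- Standard error (SE) = 1.4 × √(1/42 + 1/43) = 0.304
- Noncentrality = difference / SE: 1.0/0.304 = 3.29; 0.73/0.304 = 2.40
- Noncentral t power, 83 degrees of freedom: 90.2% at 1.0; 66.1% at 0.73; 65.5% at 0.725

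The plan's 90% and 65% are reproduced. A one-sided test gives 94.7% and 77.0%, which does not match.

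**3. Effect of losing RHIs, same formula.** The documents give no loss rate, so the reduced counts are assumptions.

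| RHIs analysed | Assumed loss | Power at 1.0, SD 1.4 | Power at 0.73, SD 1.4 | Largest SD that keeps both stated figures (approx.) |
|---|---|---|---|---|
| 85 | none | 90% | 66% | 1.4 |
| 76 | about 10% | 87% | 61% | 1.32 |
| 68 | 20% | 83% | 56% | 1.25 |
| 60 | about 30% | 78% | 51% | 1.17 |

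With an SD of 1.3, 76 RHIs give 91% and 68%; with an SD of 1.2, 68 give 92% and 70%. The plan also cites an SD of 0.5 in a healthy population, at which power is close to 100% for any number from 60 to 85. Covariate adjustment that lowered the residual variance would act in the same direction.

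**4. Size of a missing-RHI bias, with assumed inputs.** Shift in the group difference = (number missing / arm size) × (gap between the mean of the missing and the mean of the observed), with losses in one arm only.

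- 4 of 42 missing, gap 0.7: 4/42 × 0.7 = 0.067
- 8 of 42 missing, gap 0.7: 8/42 × 0.7 = 0.133
- 8 of 42 missing, gap 1.4 (a full SD): 8/42 × 1.4 = 0.267

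The middle case is 0.133/0.304 = 0.44 of a standard error and 0.133/0.73 = 18% of the difference the plan calls clinically important. The last is 0.267/0.304 = 0.88 of a standard error, but it requires one-sided losses of 19% in patients a full SD away from the rest.

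**The case for a change.** The best case for a change is that the analysis set governs the primary result and should be fixed before the data are seen. The protocol does not say when inability to lie still is judged, so a patient who cannot complete the ICU examination could be called either excluded or missing. Rewording would cost a sentence or two and no extra patients or procedures. Even on the narrow reading, the power statement makes no allowance for loss.

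Part of this stands. The population sentence is imprecise, the modification is undefined, and the treatment of a missing RHI is left unwritten. It is also true that 90% and 65% assume 85 usable RHIs at an SD of 1.4.

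The rest does not carry a change. The sentence has the substudy as its subject, and Research Design and Methods has already said who belongs to it, so the narrow reading is the natural one. The study solution is blinded, which makes arm-specific failure to measure less likely, though not impossible, and nothing in the documents points to it. The number of patients is capped by SHARP, so restating power alters no design decision.

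A prespecified sensitivity analysis that imputes fixed values when missingness differs by arm would also gain little. Equal missing rates with different reasons would not trigger it. Single-value imputation also understates uncertainty: with 8 of 42 set to the arm mean, the reported standard error is about 0.289, against 1.4 × √(1/34 + 1/43) = 0.321 from the observed data, about 10% too small.

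Whether 85 is SHARP's total or the number still to enrol is a fair query, but these documents cannot answer it and it shows no error.

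**Conclusion.** This is a minor ambiguity of wording and a missing detail, not an error in the analysis, and no change to the plan is called for. The primary comparison uses the same patients on either reading of the population sentence, because only those with an RHI can enter the regression. The natural working convention is the one a trial statistician would adopt anyway: substudy participants with a usable postoperative RHI, analysed as randomized, with missing RHIs and their reasons shown by arm.

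Both stated power figures are correct for the inputs given. An assumed 10% loss would cost about 3 points at a difference of 1.0 (90% to 87%) and 5 points at 0.73 (66% to 61%); an SD of about 1.32 or less would cancel that. Net power may be higher or lower than stated.

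The conclusion assumes that SHARP patients outside the substudy have no RHI (the document describes SHARP as a trial of kidney function and coagulation, but its protocol is not available here), that the test is two-sided with near-equal arms, and that missing RHIs are not heavily concentrated in one arm. Marked imbalance in missing RHIs would show in by-arm counts and would then limit interpretation.

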### ***Primary analysis***

We will estimate the albumin effect on RHI using multivariable linear regression adjusting for imbalanced patient and procedure characteristics. Though we expect RHI to be normally distributed, appropriate transformations will be made if this is not the case (e.g., log transformation). If transformations are not successful, we will use nonparametric methods (i.e., Wilcoxon rank-sum test).

